6.4. Covariates and Subgroups

This protocol defines a subgroup analysis to summarize HAI, NAI, and Neut antibody titers against vaccine strains by baseline seropositive status and previous vaccination by seasonal influenza vaccine as defined for stratification (Either 2017-2018 or 2018-2019, Neither 2017-2018 or 2018-2019). As this study is not adequately powered to perform subgroup analyses, these subgroup analyses will be used for exploratory purposes only.

6.5. Missing Data

All attempts will be made to collect all data per protocol. As missing data are expected to be minimal, no imputation will be performed for missing values. Any data point that appears to be erroneous or inexplicable based on clinical judgment will be investigated as a possible outlier. If data points are identified as outliers, sensitivity analyses will be performed to examine the impact of including or excluding the outliers. Any such analysis will be reported and substantive differences will be described.

6.6. Interim Analyses and Data Monitoring

Interim analyses will only be used to terminate this trial in the event that unanticipated safety events deemed to be of sufficient concern require such action by the sponsor. These assessments will not be made on the basis of testing a formal statistical hypothesis; therefore, p-value adjustment will not be made to any analyses. A DSMB will be convened by DMID to review study progress and participant, clinical, safety, and reactogenicity and immunogenicity data.

An expedited report of safety data through Day 57 and HAI, NAI, and Neut data against 2018/2019 QIV strains and heterologous strains from baseline (Day 1) and Day 29 unblinded by study arm will be prepared in Section 6.2.1; though this report will be released while subjects remain in the trial for long-term safety and immunogenicity follow-up, it will be considered the final analysis of these data.

Emergent public health needs may dictate additional interim safety, reactogenicity, and/or immunogenicity analyses be performed on available information at any time during the trial. If this occurs, immunogenicity data will be analyzed as results are available from the central immunogenicity laboratory.

6.6.1. Interim Safety Review

An interim safety review may include enrollment and demographic information, medical history, concomitant medications, physical assessments, clinical laboratory values, dosing compliance, and solicited and unsolicited AE/SAEs. Additional data may be requested by the DSMB, and interim statistical reports may be generated as deemed necessary and appropriate by DMID. The DSMB may receive data in aggregate and presented by study arm, including expected and observed rates of the expected AEs. The DSMB will review

grouped data in the closed session only. The DSMB will meet and review this data at scheduled time points or ad hoc as needed during this trial as defined in the DSMB charter. As an outcome of each review/meeting, the DSMB will make a recommendation as to the advisability of proceeding with study vaccinations (as applicable), and to continue, modify, or terminate this trial.

Additionally, this trial will be monitored to determine if any of the halting rules described in Section 9.5 of the protocol are met.

6.6.2. Interim Immunogenicity Review

There is no plan to halt this trial prior to full enrollment and completion of all follow-up visits based on interim immunogenicity results. An Expedited Interim Immunogenicity Report of HAI, NAI, and Neut serum antibody responses will be generated as described in Section 6.2.

Immune responses will be summarized in terms of strain-specific 2018/2019 QIV HAI, NAI, and Neut antibody titers and the relationship to study arm. All analyses will be carried out in parallel for all assays and provided in the expedited report. Interim analyses will focus on rates of titers $\geq 1:40$, seroconversion (see definition in Section 3.2), GMFRs, and GMTs, along with corresponding 95% confidence intervals. No formal hypothesis testing will be included in the interim analysis. All interim analyses will use the mITT population.

Tables to be included in the Expedited Report are indicated with the symbol * in the title. These include Table 21, Table 22, Table 23, Table 24, Table 25, Table 26, Table 27, and Table 28 for HAI antibodies against 2018/2019 QIV strains; Table 29, Table 30, Table 31, Table 32, Table 33, Table 34, Table 35, and Table 36 for Neut antibodies against 2018/2019 QIV strains; Table 55, Table 56, Table 57, Table 58, Table 59, Table 60, Table 61, and Table 62 for NAI antibodies against 2018/2019 QIV strains presenting summaries and 95% CIs by study arm. Additionally, HAI, NAI, and Neut results against heterologous strains will be presented starting with Table 81 and ending with Table 110.

6.7. Multicenter Studies

Randomization was stratified by site, but data will be pooled across all clinical sites for all analyses. Center effects are not anticipated because the sites use standardized procedures for vaccination and assessment of solicited and unsolicited AEs, and the study relies on a central laboratory for immunogenicity assessments.

6.8. Multiple Comparisons/Multiplicity

This study was designed to obtain preliminary estimates of safety and immune response to 2018/2019 Fluzone and Flublok vaccines with or without AF03 or Advax-CpG55.2 adjuvants in healthy adults. The study was not designed to test any specific null hypothesis, and as such no adjustment for multiple comparisons will be performed.

7. STUDY SUBJECTS

7.1. Disposition of Subjects

[Table 11](#) will present a summary of the reasons that subjects were screened but not enrolled.

The number and percentage of enrolled subjects excluded from each analysis population by study arm are presented in [Table 12](#). A listing of subjects excluded from each analysis population will be presented in [Listing 5](#).

The disposition of subjects in the study will be tabulated by study arm ([Table 13](#)). The table will show the total number of subjects screened, randomized, receiving the first study vaccination, receiving the second study vaccination, completing the blood draw for the primary immunogenicity endpoints, and completing the last visit.

A flowchart showing the disposition of study subjects, adapted from the CONSORT Statement [2] will be included and will present the number of subjects screened, randomized, lost to follow up, and analyzed, by study arm ([Figure 1](#)).

A listing of subjects who were discontinued from treatment or terminated from study follow-up and the reason will be included in [Listing 2](#).

7.2. Protocol Deviations

A summary of subject-specific protocol deviations will be presented by the deviation category and deviation type, and study arm for all enrolled subjects ([Table 6](#)). Major deviations that will be reviewed for possible exclusion of immunogenicity results from the PP population including deviations related to eligibility/enrollment, treatment administration schedule, follow-up visit schedule, and receipt of exclusionary vaccines or medications. All subject-specific protocol deviations and non-subject-specific protocol deviations will be included in [Listing 3](#) and [Listing 4](#).

8. IMMUNOGENICITY EVALUATION

Immunogenicity data summaries and analysis for primary and secondary endpoints will be presented for the mITT and PP populations. Immune responses in terms of strain-specific 2018/2019, 2019/2020 QIV HAI, NAI, and Neut antibody titers will be summarized by study arm at each time point. Descriptive summary statistics will be provided for all assays and time points including number of subjects with non-missing results, percentage of subjects with titers $\geq 1:40$ for HAI and Neut only, percentage of subjects achieving seroconversion, GMTs along with corresponding 95% CI, and GMFRs along with corresponding 95% CI. Exact confidence intervals using the Clopper Pearson method will be presented for proportional endpoints. Ratios of GMTs along with their 95% CIs between adjuvanted and unadjuvanted groups will be presented at each timepoint. Confidence intervals using the Delta Method will be provided for the ratio of GMTs.

Individual HAI, NAI, and Neut assay results will be provided in [Listing 9](#), [Listing 10](#), and [Listing 11](#). Individual exploratory assay results will be provided in [Listing 12](#), [Listing 13](#), and [Listing 14](#) for memory B cells, [Listing 15](#) for Tfh cells, [Listing 16](#) for plasmablasts, [Listing 17](#) for neutralizing fc-effector, [Listing 18](#) for antibody forensics, and [Listing 19](#) for NA ELISA.

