## **11 STATISTICAL CONSIDERATIONS**

### **11.1 Introduction**

The goal of this clinical study is to assess, in healthy adults ages 18-45, the safety, reactogenicity and immunogenicity of either the 2018/2019 seasonal Fluzone or Flublok QIV manufactured by Sanofi Pasteur administered intramuscularly given without adjuvant or with one of two adjuvants, AF03 or Advax-CpG55.2. These study arms are included to allow evaluation of the potential of each of the two adjuvants to enhance the immune response to either the 2018/2019 seasonal Fluzone QIV or the 2018/2019 seasonal Flublok QIV.

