**Table 11: Precision of Binomial Confidence Intervals**

N	95% CI
4	6-94
6	11-89
40	33 -67
60	36-64
120	40-60
240	43-57

For each of the primary immunogenicity objectives, a power analysis is provided below for testing the following hypotheses with the planned sample size, where  $p_c$  = proportion of responders in comparator arm; where  $p_e$  = proportion of responders in experimental arm.

Test for difference in proportion responders:

$H_0: p_c - p_e = 0$  – No difference in proportion responders

$H_1: p_c - p_e \neq 0$  – difference in response rates

[Table 12](#) illustrates the minimum detectable differences in the proportion of subjects responding (e.g., attaining seroconversion or a titer  $\geq 1:40$ ) between two adjuvanted treatment arms using a two-sided Likelihood Ratio Test and  $\alpha = 0.05$ . It is assumed that approximately 3% of the

subjects (N=2) in each treatment arm will be excluded from the per protocol analysis of primary immunogenicity endpoints leaving N=38 subjects per treatment arm. If Advax-CpG55.2 is unavailable, approximately 3% of the subjects (N=2) in each treatment arm will be excluded from the per protocol analysis of primary immunogenicity endpoints leaving N=58 subjects per treatment arm. Seroconversion rates of 40% to 90% are considered.

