**Table 12: Minimum Detectable Difference in Proportion Responders with 80% Power**

Assumed Proportion of subjects with titer $\geq 40$ in comparator arm ( $p_c$ )	Minimum detectable difference in response rate ( $p_c - p_e$ ), N=38 per group	Minimum detectable difference in response rate ( $p_c - p_e$ ), N=58 per group
0.40	0.32	0.26
0.50	0.30	0.25
0.60	0.28	0.23
0.70	0.24	0.20
0.80	0.18	0.16
0.90	0.10	0.10

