5. SAMPLE SIZE CONSIDERATIONS

This study is planned to enroll a total of 40 subjects in each group. This study is not designed to test a formal null hypothesis. Rather, it is intended to obtain sufficient data to obtain meaningful estimates of the immune response and to uncover any safety issues that occur at a sufficiently high rate that they might be observed in a study of this size. As such, the type one error rate, $\alpha = 0.05$, is not adjusted for multiple comparisons. While this study is not designed to test any specific null hypothesis, the following tables illustrate the precision and power that is available for select estimates and comparisons of interest.

[Table 3](#) indicates the probability of observing one or more safety events, such as solicited injection site or systemic reactogenicity events or an unsolicited non-serious AE of a particular type for sentinel subjects (N=4 or 6), for a single adjuvanted/ unadjuvanted study arm/stratum (N = 40 or 60), for all subjects receiving the same seasonal QIV (N= 120), for all subjects in the trial (N=240).

Binomial confidence intervals (CI) are widest (have the least precision) when the response rate is 50%.

[Table 4](#) is presented to indicate the worst-case scenario for precision of observed exact (Clopper-Pearson) binomial confidence intervals.

[Table 5](#) illustrates the minimum detectable differences in the proportion of subjects responding (e.g., attaining seroconversion or a titer $\geq 1:40$) between two adjuvanted study arms using a two-sided Likelihood Ratio Test and $\alpha = 0.05$.

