8.2. Secondary Immunogenicity Analyses

The secondary immunogenicity endpoints HAI, Neut and NAI seroconversion, percentage of subjects with titer $\geq 1:40$ for HAI, GMFRs, GMTs, and ratios of GMTs (between adjuvanted group and unadjuvanted) against the 2019/2020 QIV strains 28 days after vaccination with the 2019/2020 QIV (Day 118) will be summarized as described above. HAI and Neut seroconversion, percentage of subjects with HAI titers $\geq 1:40$, GMFRs, GMTs, and ratios of GMTs for HAI and Neut against heterologous influenza A/H3 strains on approximately Days 8, 29, 57, 90, and 118 after study vaccination with the 2018/2019 QIV will be also presented. HAI, Neut and NAI seroconversion, percentage of subjects with HAI and Neut titers $\geq 1:40$, and GMTs against the 2018/2019 QIV strains on approximately Days 8, 29, 57, 90, and 118 after study vaccination will be presented. HAI, Neut, and NAI GMFRs against the 2018/2019 QIV strains on approximately Day 57 and Day 90 will also be presented. NAI seroconversion, NAI GMTs and ratios of NAI GMTs against heterologous N1 and N2 NA antigens will also be assessed on approximately Days 8, 29, 57, 90, and 118 for study groups 1, 2 and 3. No formal hypothesis testing is planned.

Secondary summaries for the 2019/2020 QIV strains are provided in [Table 69](#), [Table 70](#), [Table 71](#), [Table 72](#), [Table 73](#), [Table 74](#), [Table 75](#), [Table 76](#), [Table 77](#), [Table 78](#), [Table 79](#), and [Table 80](#). Summaries of HAI, and Neut against heterologous H3 Influenza strains for both mITT and PP populations will also be provided in [Table 81](#), [Table 82](#), [Table 83](#), [Table 84](#), [Table 85](#), [Table 86](#), [Table 87](#), [Table 88](#), [Table 89](#), and [Table 90](#) for HAI, and [Table 91](#), [Table 92](#), [Table 93](#), [Table 94](#), [Table 95](#), [Table 96](#), [Table 97](#), and [Table 98](#) for Neut. Summaries of NAI against heterologous N1 and N2 antigens will be presented in [Table 99](#), [Table 100](#), [Table 101](#), [Table 102](#), [Table 103](#), [Table 104](#), [Table 105](#), [Table 106](#), [Table 107](#), [Table 108](#), [Table 109](#), and [Table 110](#).

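### The binary primary immunogenicity endpoints have no planned between-arm difference with an interval, although the power table is written for that difference

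*SAP*

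**What the plan says.** Protocol 11.1 says the study arms are included "to allow evaluation of the potential of each of the two adjuvants to enhance the immune response". In Protocol 11.4.3 the power calculation is introduced with "For each of the primary immunogenicity objectives, a power analysis is provided below for testing the following hypotheses with the planned sample size". It sets a null hypothesis of no difference in responder proportions against a two-sided alternative. Table 12, titled "Minimum Detectable Difference in Proportion Responders with 80% Power", gives detectable differences for comparator rates from 0.40 to 0.90 with 38 or 58 subjects per arm. The text describes the contrast as "between two adjuvanted treatment arms using a two-sided Likelihood Ratio Test" at α = 0.05. SAP 5 and SAP Table 5 repeat this.

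Both documents qualify the calculation. Protocol 11.2 and 11.4.3 and SAP 5 say the study is not designed around a formal null hypothesis and present the tables as illustrations of precision and power. Protocol 11.2 also says, however, that the sample size supports formal testing of selected hypotheses.

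For the analysis, SAP 8 states: "Exact confidence intervals using the Clopper Pearson method will be presented for proportional endpoints". It then plans GMT ratios with 95% CIs between adjuvanted and unadjuvanted groups. SAP 8.1 applies this to the Day 29 primary endpoints, with mITT as the primary population. Shells 21–36 (HAI, Neut) and 53–60 (NAI) have a seroconversion row and, for HAI and Neut, a titer ≥1:40 row. Each is filled arm by arm, and neither has a difference or ratio row. Protocol 11.6.3 plans the same quantities.

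**The concern.** The trial asks whether an adjuvant raises the response, and the power table expresses that question as a difference in responder proportions. The planned tables do not report that difference with its uncertainty. A reader who wants to know how many more subjects seroconvert with AF03 than without it can subtract two percentages, but then has only two separate intervals to judge the result by. Comparing separate intervals by eye is much more conservative than an interval for the difference, so a real gain in responders could be read as inconclusive.

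The omission also stands out within the SAP. GMTs have a between-arm ratio with an interval. Binary solicited events are compared between arms by logistic regression with odds ratios, 95% CIs and p-values (SAP 9.3.1, shells 120–121). The binary immunogenicity endpoints have neither.

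The power text has two further faults. It names two adjuvanted arms, which is not the contrast the GMT ratios make. One of its cells also claims power that cannot be reached.

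**Working it through.** **Inputs.** α = 0.05 two-sided, likelihood ratio test (LRT), 80% power, N = 38 or 58 per arm, and p_c from 0.40 to 0.90 (Protocol 11.4.3, Table 12; SAP 5, Table 5).

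**Step 1: reproduce the plan's figures.** With p̄ = (p_c + p_e)/2, the LRT noncentrality is

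λ = 2n[p_c ln(p_c/p̄) + (1−p_c) ln((1−p_c)/(1−p̄)) + p_e ln(p_e/p̄) + (1−p_e) ln((1−p_e)/(1−p̄))],

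and power = Φ(√λ − 1.96) + Φ(−√λ − 1.96).

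Example: n = 38, 0.40 versus 0.72, p̄ = 0.56. The bracket is −0.1346 + 0.1861 + 0.1810 − 0.1266 = 0.1059, so λ = 76 × 0.1059 = 8.05, √λ = 2.84 and power = 0.81.

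Solving for 80% power with p_e above p_c gives:

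| p_c | N=38 stated | N=38 solved | N=58 stated | N=58 solved |
|---|---|---|---|---|
| 0.40 | 0.32 | 0.316 | 0.26 | 0.258 |
| 0.50 | 0.30 | 0.303 | 0.25 | 0.250 |
| 0.60 | 0.28 | 0.277 | 0.23 | 0.232 |
| 0.70 | 0.24 | 0.239 | 0.20 | 0.203 |
| 0.80 | 0.18 | 0.185 (0.1845) | 0.16 | 0.162 |
| 0.90 | 0.10 | no solution | 0.10 | 0.099 |

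Eleven of the 12 cells reproduce. The column label is p_c − p_e, but the values match p_e > p_c.

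**Step 2: the cell that fails.** At p_c = 0.90 a difference of 0.10 puts p_e at 1.00, the ceiling. The bracket is −0.0487 + 0.0693 + 0.0513 = 0.0719, so λ = 5.47, √λ = 2.34 and asymptotic power is 0.65.

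For exact power, all 38 experimental subjects respond, and the result depends only on m, the number of comparator non-responders. The LRT statistic is 2.83 at m = 2 and 4.28 at m = 3, against a critical value of 3.84, so it rejects when m ≥ 3. With m ~ Bin(38, 0.10), power = 1 − (0.0182 + 0.0770 + 0.1584) = 0.746. No larger difference exists, so 80% is out of reach at N = 38.

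**Step 3: one-arm intervals against an interval for the difference.** Take 15/38 versus 27/38, the whole-number counts nearest to 0.40 versus 0.72.

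- Clopper-Pearson: 24.0–56.6% and 54.1–84.6%. They overlap.
- Difference: 27/38 − 15/38 = 0.316.
- Wilson limits: 0.256–0.553 for 15/38 and 0.552–0.830 for 27/38.
- Newcombe lower limit: 0.316 − √[(0.711−0.552)² + (0.553−0.395)²] = 0.09.
- Newcombe upper limit: 0.316 + √[(0.830−0.711)² + (0.395−0.256)²] = 0.50.

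The difference interval excludes 0 although the arm intervals overlap. The same happens with 40 per arm: for 16/40 versus 29/40 the Clopper-Pearson intervals are 24.9–56.7% and 56.1–85.4%, while the difference is 0.325 (0.108 to 0.503).

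**Step 4: how far an overlap reading would mislead.** These figures come from exact enumeration at N = 38, using Table 12's differences for p_c = 0.40 to 0.80.

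- The LRT has power 0.80–0.82.
- The two Clopper-Pearson intervals fail to overlap with probability 0.45, 0.41, 0.43, 0.38 and 0.28, and with probability about 0.003 under the null.
- The Newcombe interval excludes 0 with probability 0.80–0.82 for p_c 0.40–0.70 and 0.73 at 0.80. Its mean full width is about 0.29–0.40.

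**Step 5: number of intervals the fix adds.** HAI and Neut have 2 endpoints × 4 strains each, and NAI has 1 × 4, giving 8 + 8 + 4 = 20 endpoints. Four contrasts × 20 = 80 intervals per population. Under no effect, about 5% of 80 = 4 would exclude 0.

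**The case against.** The plan delivers its endpoints as defined. Protocol Table 1 and SAP 3.1 define seroconversion and titer ≥1:40 as percentages for each study group; only the GMT ratio is defined as a between-group quantity. Protocol Table 11 illustrates one-arm Clopper-Pearson precision, which is exactly what SAP 8 presents. The SAP therefore departs from neither the outcome definitions nor Protocol 11.6.3. This stands, and it makes the point an improvement to the plan and not a breach of it.

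Four stronger readings are tempting, and the documents do not support them.

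- A reader might infer that the SAP never compares proportions between arms. It does so for solicited events, which are a primary safety outcome.
- A reader might infer that the adjuvant effect is not estimated. GMT ratios with CIs estimate it on the titer scale, and a point difference in proportions can be read off the tables. What is missing is its interval.
- A reader might infer that the sample size rests on a test that was then dropped. The power table is labelled illustrative and formal testing is disclaimed. SAP 8.2 adds "No formal hypothesis testing is planned", although that sentence concerns the secondary endpoints. Protocol 11.2 is mixed on testing, which is a reason to clarify the wording and not proof of a contradiction.
- A reader might infer that the planned analysis has only 28–45% power. Those figures belong to an overlap rule that appears nowhere in the plan. They show only that overlap is a poor substitute for a difference interval.

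**Conclusion.** The point holds as a missing interval. The documents illustrate power for a between-arm difference in responder proportions, yet no between-arm effect measure with a CI is planned for seroconversion or titer ≥1:40. The GMT ratio does not show how many more subjects respond. The per-arm intervals cannot supply that uncertainty: at 38 per arm they can overlap when the difference is 0.32 with a 95% CI of 0.09 to 0.50.

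Two corrections to the power text go with this. The arms it names do not match the planned adjuvanted-versus-unadjuvanted contrasts. The cell for p_c = 0.90, N = 38 cannot reach 80%; exact LRT power at the ceiling is about 0.75.

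The illustration uses the per-protocol figure of 38, whereas SAP 8.1 makes mITT primary; 40 per arm leads to the same conclusion. The worked intervals are Newcombe and the recommended ones are Miettinen-Nurminen. Both are score-type intervals, but the exact limits will differ. Because the trial is a descriptive Phase I study, this is a worthwhile low-cost change and does not put the design in question.

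**What to change.** 1. In SAP 8 and 8.1 and shells 21–36 and 53–60, add at Day 29 the difference in percentage seroconverting and, for HAI and Neut, in percentage with titer ≥1:40. Take it as adjuvanted minus corresponding unadjuvanted (Groups 2−1, 3−1, 5−4, 6−4), with a 95% score (Miettinen-Nurminen) CI, labelled as estimation only. Protocol 11.6.3 has the same gap and should be aligned if it is amended.
2. In Protocol 11.4.3 and SAP 5, describe the power contrast as an adjuvanted arm against its unadjuvanted comparator.
3. In Protocol Table 12 and SAP Table 5, mark the p_c = 0.90, N = 38 cell as not attainable at 80% power.

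The cost is one or two rows per shell, one added SAP sentence and the two text corrections. No new data, subjects or tests are needed. The downside should be stated in the SAP: about 80 unadjusted intervals per population, of which about 4 would exclude zero by chance if there were no effect, so they are to be read descriptively.
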